## 7 HUMAN SUBJECTS PROTECTIONS

### 7.1 RATIONALE FOR SUBJECT SELECTION

- 7.1.1 AR-PCNSL is a rare disease. HIV-infected individuals are at increased risk of this lymphoma. The purpose of the study is to investigate therapy that avoids late-occurring neurocognitive toxicities associated with WBRT. Selection of individuals with favorable survival prospects from the standpoint of the underlying HIV disease is essential in order to study late occurring treatment toxicities for this disease. Therefore, patients who have resistant HIV that cannot be suppressed and would therefore not be able to have immunologic recovery (thought essential to maintaining the lymphoma in remission), will not be appropriate subjects for this trial. Additionally, up to 3 patients who do not adhere to HAART and have high HIV viral loads (see section 6.1.3) without immune recovery and have a lymphoma relapse within the first 9 months may be replaced as subjects.
- 7.1.2 Strategies for recruitment will include announcements on the World Wide Web (see [Appendix 8](#)) as well as letters to referring physicians and AIDS treatment bulletins.
- 7.1.3 Pregnancy is excluded on the basis of the overall toxicity expected from the treatment, which would likely threaten fetal viability and potentially increase the risk to the mother and the potential teratogenicity of high-dose methotrexate.
- 7.1.4 Exclusion of patients less than 18 years of age is based on the extreme rarity of this disease in children. Inclusion of children on the study would result in such an

insufficient number that it would not be possible to evaluate the therapy relative to the purpose of the study.

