Neurocognitive preservation is central to the goals of this clinical investigation, and serial neuropsychometric testing will be performed on patients. Since at the time of presentation patients are expected to have tumor related cognitive impairment, baseline neuropsychometric testing will be performed within the first two months of the time of complete tumor response. Repeat testing will be performed every 3 to 6 months up to 2 years following end of treatment, and then again at 3 years. Such measures have been found to be useful in PCNSL patients for assessing neurocognitive functioning over time.

The protocol will also assess patients from the standpoint of the underlying HIV infection. Since justification for pursuing non-radiation-based therapy is that HAART may improve survival such that patients live long enough to experience radiation-induced brain injury, patients with multidrug resistant HIV not amenable to suppression will not be eligible for the study, because a meaningful lasting immune recovery will not be feasible. Thus, immune parameters such as the CD4+ and CD8+ cell counts, HIV viral loads, HIV resistance mutations, and HAART adherence will be recorded. Patients who fail to maintain low HIV viral loads and as a consequence experience other HIV-related complications that can affect neurocognitive function will be censored as soon as this becomes evident, and such patients can be replaced, as discussed in the statistical section of the protocol.

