3.11.2 Off Study Criteria

- Refusal to adhere with HAART
- Refusal of oncologic therapy
- Patient or patient advocate (if patient not competent) voluntary withdrawal
- Progression of disease and either refusing or not eligible to receive second-line chemotherapy AND/OR radiotherapy
- Progressive, irreversible neurocognitive deficits, not attributed to AIDS-PCNSL or treatable infection, occurring greater than 90 days after the completion of

radiation therapy that would be scored as grade 3 or higher by the RTOG/EORTC Late Radiation Morbidity Scoring Scheme

- Completion of 5 years follow-up with no recurrent AR-PCNSL

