## 5.3 RESPONSE CRITERIA

Response criteria are based on published standards for phase II studies of supratentorial malignant glioma and a modification of the response assessment of aggressive non-Hodgkin's lymphoma by integrated international workshop criteria and fluorine-18 – fluorodeoxyglucose positron emission tomography, and an international workshop to standardize baseline evaluation and response criteria for primary CNS lymphoma. Cross-sectional measurements of tumors will be used to assess baseline and responses.

- 5.3.1 Complete Response - disappearance of all enhancing lesions on MRI of the brain, negative FDG-PET scan persisting for at least 4 weeks in patients who were off corticosteroids, negative CSF cytology and neurologically improved from baseline.
- 5.3.2 Complete Response Unconfirmed (CRu) – either a CRu, PR or SD by MRI criteria with a completely negative FDG-PET off steroids, and negative CSF cytology. If there is no evidence of progression while off steroids for 4 months, response will be reclassified as CR.
- 5.3.3 Partial Response
  - 5.3.3.1 A reduction of enhancing tumor volume by more than 50% maintained for at least 4 weeks, steroids stable or reduced, and neurologically stable or improved with positive FDG-PET, or

- 5.3.3.2 Normalization of MRI, negative FDG-PET, but with persistent disease by CSF cytology.
- 5.3.4 Progressive disease - an increase of tumor volume of more than 25% or occurrence of new lesions, or neurologically worse, steroids stable or increased.
- 5.3.5 Stable disease – not meeting the criteria for complete response, partial response, or progressive disease and with a positive FDG-PET
- 5.3.6 Treatment failure - progressive or stable disease, relapse after initial response, death, or discontinuation of chemotherapy because of complications or because of patient's or Investigator's decision. Patients who require radiotherapy will be considered treatment failures for purposes of the protocol, regardless of long-term outcome.
- 5.3.7 Substantial brain dysfunction and cognitive problems (as referred to in sections 1.2.3 and 7.4.4) that will define treatment failure refer to post-treatment recurrent brain lymphoma, treatment related functional brain pathology, and/or neurologic function class 3 or 4 as defined in Appendix 2: Neurological Function Class.

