#### 6.1.3 Sample Size and Accrual Limits

The primary objective of this study is to preliminarily estimate the magnitude of, and determine if there is potentially an acceptable fraction of, patients with primary brain lymphoma, who will receive the experimental treatment consisting of HAART with high-dose methotrexate-rituximab who are able to survive without recurrent lymphoma or severe cognitive problems (as defined by Neurological Function Class 3 in [Appendix 2](#)) for at least two years.

The goal of this limited size pilot trial is to enroll 15 evaluable patients who receive all treatment, including high-dose methotrexate. With conventional treatments, including whole brain irradiation, it would be expected that only 25-30% of all such patients with this disease would be alive without recurrent brain lymphoma and free of cognitive problems at the end of two years (a satisfactory result, but in too small a fraction of patients). We believe it quite possible that by using this particular chemotherapy, as many as 65% would be alive without recurrent lymphoma and without cognitive problems after two years. Sixty five percent is a figure chosen that is within range of the outcome expected in high-risk patients with non-AIDS primary brain lymphoma treated with high-dose methotrexate based strategies. With 15 patients, using a one-sided 0.1 alpha level exact test of binomial proportions, there is 88% power to rule out 30% with a satisfactory result after two years in favor of 65% with a satisfactory result. Should the results appear at all promising, even if not to this degree, the strategy may be taken to the AIDS Malignancy Consortium to see if they are interested in pursuing the idea in a larger, more definitive fashion. The results of this study will be weighed against the best available data from other studies to make a reasonable determination as to how to proceed with or modify this approach for further development.

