Additionally, up to 10 additional patients who are not eligible to receive high-dose methotrexate may be accrued in the “Radiation-sparing Best Available Care” Cohort. The patients enrolled in this limited size cohort will be evaluated for the same endpoints as in the main cohort receiving high-dose methotrexate, but given the limited number of patients who will enroll into this cohort, all analyses in this cohort will be considered hypothesis generating and exploratory. Accrual to this cohort will close when 15 evaluable patients have been enrolled in the main cohort.

All secondary endpoints will be evaluated using explorative techniques, and will be reported as exploratory, since the study is not designed to address any of these points with more than minimal power.

Since part of the treatment strategy is aimed at HIV suppression and immune reconstitution, up to 3 patients who are non-adherent with HAART within the first 9 months of therapy may be replaced. It can often take up to 9 months to adjust medications for purposes of optimizing medication tolerance and adherence to antiretroviral therapy. Patients who are clearly non-adherent and thus are unable to maintain an HIV viral load of <5000 copies HIV mRNA/mL plasma and do not have an increment in the CD4+ cells to above 75/mm^3 by the end of 9 months may be replaced. Patients who maintain lower HIV viral loads but do not have adequate immune recovery will not be replaced, and will be considered treatment failures in the event of tumor recurrence. Informal comparison will be made between those who are HAART naive at entry and those who are antiretroviral experienced.

This is a rare condition, and it is expected to take between 6 and 10 years to enroll 15 patients onto this trial in the main cohort and up to 10 in the cohort not receiving high-dose methotrexate. Up to three patients may be replaced if during the first 9 months they are clearly non-adherent with HAART as described above. Thus an accrual ceiling of 28 patients will be used.

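### Sections 1.2.5, 6.1.3 and 7.1.1 give different rules for replacing HAART-non-adherent patients, and 7.1.1 admits only patients who have already relapsed, which can bias the two-year success fraction upward

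*Combined protocol and SAP*

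**What the plan says.** Three sections of the combined protocol and SAP describe replacement.

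- **6.1.3 (Sample Size and Accrual Limits):** "up to 3 patients who are non-adherent with HAART within the first 9 months of therapy may be replaced". The patient must be clearly non-adherent, with viral load not held below 5000 copies/mL and CD4+ count not above 75/mm³ by the end of 9 months. Relapse is not mentioned. By contrast, "Patients who maintain lower HIV viral loads but do not have adequate immune recovery will not be replaced", and these patients count as failures if the tumour recurs.
- **7.1.1 (Rationale for Subject Selection):** up to three patients who do not adhere and have high viral loads "without immune recovery and have a lymphoma relapse within the first 9 months may be replaced as subjects". It cites 6.1.3, but the relapse condition is its own.
- **1.2.5 (Novel Tumor Assessment and Psychometric Testing):** patients who lose viral control and then have HIV complications that can affect neurocognition "will be censored as soon as this becomes evident, and such patients can be replaced". It names neither non-adherence nor relapse, and refers to the statistical section.

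Four other places bear on the point. Section 5.3.6 counts as treatment failure "relapse after initial response, death, or discontinuation of chemotherapy because of complications", among other events, with no exception for non-adherence. Section 3.11.2 makes "Refusal to adhere with HAART" an off-study criterion. Section 6.1.3 sets the target: "The goal of this limited size pilot trial is to enroll 15 evaluable patients who receive all treatment". It also sets the test: "using a one-sided 0.1 alpha level exact test of binomial proportions, there is 88% power" to rule out 30% in favour of 65%.

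**The concern.** The same patient can be kept, replaced or censored depending on the section followed. A non-adherent, viraemic patient in remission at 9 months is replaceable under 6.1.3 but not under 7.1.1.

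The more serious problem is that 7.1.1 selects on the outcome. Its conditions are joined by "and" in effect: all must be met, including relapse, so everyone it makes replaceable has already failed the primary endpoint. If those patients leave the denominator, failures are exchanged for fresh draws and the success fraction can only rise.

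The trigger in 1.2.5 overlaps with the cognitive part of the endpoint, and censoring has no defined role in an exact binomial test of a two-year proportion. No section says how a patient taken off study for refusing HAART counts at two years.

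**Working it through.** **Inputs.** From 6.1.3: n = 15, one-sided exact binomial test at 0.10, null 30%, alternative 65%, conventional-treatment benchmark 25–30%, at most 3 replacements, accrual ceiling 28 = 15 + 10 + 3. The documents do not give the share of failures that would qualify for replacement, so a range is used.

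**Assumption.** Replaced patients leave the denominator, which stays at 15.

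**1. The plan's own figure.** The smallest cut-off with error at or below 0.10 is 8:
- P(X ≥ 7 | 15, 0.30) = 0.131, too large
- P(X ≥ 8 | 15, 0.30) = 0.050
- power P(X ≥ 8 | 15, 0.65) = 0.887, which agrees with the stated 88%
- at a true 25%, P(X ≥ 8 | 15, 0.25) = 0.017

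**2. Upper limit under 7.1.1.** If k failures are replaced, reaching 8 successes among the 15 counted patients is the same as reaching 8 among 15 + k treated. The error is therefore at most P(Bin(15 + k, p) ≥ 8).

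| Failures replaced (k) | True 30% | True 25% |
|---|---|---|
| 0 | 0.050 | 0.017 |
| 1 | 0.074 | 0.027 |
| 2 | 0.105 | 0.040 |
| 3 | 0.141 | 0.057 |

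With three failures replaced, the expected estimate is 18 × 0.30 / 15 = 36% at a true 30%, and about 78% at a true 65%.

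**3. Partial replacement under 7.1.1.** Each failure qualifies with probability q. At most three are replaced, and each replacement is a new draw that may itself be replaced while slots remain.

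| q (share of failures) | Error, true 30% | Expected estimate, true 30% | Expected estimate, true 65% |
|---|---|---|---|
| 5% | 0.061 | 31.1% | 66.2% |
| 10% | 0.073 | 32.2% | 67.3% |
| 15% | 0.086 | 33.2% | 68.5% |
| 20% | 0.099 | 34.0% | 69.7% |

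The error reaches 0.10 at about q = 20.4%, that is 0.204 × 0.70 = 14% of treated patients qualifying.

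**4. Under 6.1.3.** If successes and failures are replaced at equal rates, the error stays at 0.050. If successes are replaced at half the rate of failures, with 10% to 50% of failures qualifying, it is 0.061 to 0.079.

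**5. An example.** Eight successes with three relapsed patients replaced reads 8/15 = 53% (p = 0.050, positive). Counting everyone treated gives 8/18 = 44% (p = 0.141, not positive).

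**The case against.** The best counter-argument is that there is one operative rule. Sections 1.2.5 and 7.1.1 both refer to the statistical section, and only 6.1.3 gives laboratory criteria and derives the ceiling, so the other two could be loose paraphrases. This does not settle the matter. No section states that precedence, and 6.1.3 contains neither the relapse condition nor censoring. Replacement under 6.1.3 is also optional and decided at 9 months, when a relapse may already be known.

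A second argument is size. Removal from the denominator is inferred, the qualifying share is unknown, and a patient must meet four conditions within 9 months. For shares of 5% to 20% the error stays below 0.10. All of this stands, and it limits the claim about the test. It does not protect the estimate, which is the primary objective and rises with each failure replaced.

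Third, this is a pilot whose progression is not tied to the test, and an evaluable-patient analysis is a recognised phase II choice when HAART is part of the treatment. That supports reporting an adherent subset. It does not support choosing the subset by relapse.

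Finally, the censoring in 1.2.5 may be meant for the neuropsychological follow-up or the survival endpoints. That is possible; the section does not say.

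**Conclusion.** The replacement rules are inconsistent, and 7.1.1 as written selects on the primary outcome. This should be fixed before analysis.

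The upward direction under 7.1.1 is certain if replaced patients leave the denominator. That reading is not stated. It is inferred from the 15-evaluable target, the build-up of the ceiling, and the contrast in 6.1.3 with patients who are not replaced and do count as failures.

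The size is conditional. At a true 30%, the bias in the expected estimate is about 1 to 4 percentage points if 5% to 20% of failures qualify, and at most 6 points. The error exceeds 0.10 only if two or three failures are replaced and the true rate is 30%. Section 6.1.3 taken alone biases the result only as far as non-adherence tracks failure.

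**What to change.** Reconcile 1.2.5, 6.1.3 and 7.1.1 into one rule that does not depend on tumour outcome:

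- Delete the relapse condition from 7.1.1, and the censoring wording in 1.2.5 as it applies to the primary endpoint.
- State that every main-cohort patient who starts protocol therapy stays in the primary denominator with the actual outcome.
- State how a patient taken off study with unknown two-year status counts, for example as a failure.
- Add any extra patients (up to 3) to n, with the matching cut-off below.
- Report the HAART-adherent subset as a sensitivity analysis.

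| n | Cut-off | Error at 30% | Power at 65% |
|---|---|---|---|
| 15 | 8 | 0.050 | 0.887 |
| 16 | 8 | 0.074 | 0.933 |
| 17 | 9 | 0.040 | 0.901 |
| 18 | 9 | 0.060 | 0.940 |

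The number of extra patients might itself depend on outcomes already seen. Backward induction over every such choice of 0 to 3 patients with these cut-offs gives error of at most 0.083 at 30% and 0.030 at 25%, and power of at least 0.871. That worst case is slightly below the planned 88%.

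The cost is wording in three sections and possibly a slightly less favourable observed fraction. No patients beyond the ceiling of 28 are needed.

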## 7.2 PARTICIPATION OF CHILDREN

See section 7.1.4 above. The standard of care for AR-PCNSL is currently WBRT. The treatments in this protocol have uncertain efficacy, and the risk to very young children may be more than minimal while the estimates of benefit are not fully known. If the therapy appears beneficial, a risk/benefit assessment will be made for the potential enrollment of children, and if it appears reasonable to do so, consideration for amending the protocol for enrollment of children will be made.

## 7.3 PARTICIPATION OF SUBJECTS UNABLE TO GIVE CONSENT

Adults who are unable to provide initial informed consent are eligible for enrolling in this protocol as noted in Section 2.2.1.12. There is also a possibility, though unlikely, that subjects who provide initial consent could become decisionally impaired. For this reason and because there is a prospect of direct benefit from research participation (section 7.4), all subjects will be offered the opportunity to fill in their wishes for research and care, and assign a substitute decision maker on the “NIH Advance Directive for Health Care and Medical Research Participation” form so that another person can make decisions about their medical care in the event that they become incapacitated or cognitively impaired during the course of the study. Note: The PI or AI will contact the NIH Ability to Consent Assessment Team for evaluation. For those subjects that become incapacitated and do not have pre-determined substitute decision maker, the procedures described in MAS Policy 87-4 for appointing a surrogate decision maker for adult subjects who are (a) decisionally impaired, and (b) who do not have a legal guardian or durable power of attorney, will be followed.

## 7.4 EVALUATION OF BENEFITS AND RISKS/DISCOMFORTS

- 7.4.1 The investigational nature and objectives of this trial, the procedures and treatments involved and their attendant risks and discomforts, potential benefits, and potential alternative therapies will be carefully explained to the patient or the patient’s surrogate, and a signed informed consent document will be obtained.
- 7.4.2 The potential benefit is that the protocol therapy may result in specific control of AR-PCNSL in those patients to whom it is administered and potentially avoid the late occurring neurotoxic effects associated with WBRT.
- 7.4.3 The potential risk is that the protocol therapy may be toxic, and/or be ineffective. It is not known whether in AIDS, high-dose methotrexate will cause CNS damage, though the limited available data suggests that it does not cause excess neurological damage. The treatment requires up to 6 or more in-patient admissions that are likely to last 7 days or longer on each admission. Additionally, the staging and restaging requirements of the study requires frequent, sometimes invasive, evaluations. Thus, the time commitment and potential morbidity associated with tumor biopsy represents a potential risk and discomfort to study participants.
- 7.4.4 Discussion of risks to subjects in relation to anticipated benefits and the

importance of the knowledge that may reasonably be expected from the results: as outlined in the introduction, the standard of care for AR-PCNSL is predicted to cause serious brain dysfunction in patients who survive long enough for late-occurring radiation neurotoxic effects to manifest. The median time to cognitive decline following WBRT in high risk populations is 12-18 months. This study is aimed at developing a strategy toward long-term remission of AR-PCNSL in part through novel relatively non-lymphocytotoxic chemotherapeutic approaches and in part through efforts at immune reconstitution.

## 7.5 SPECIMEN HANDLING GUIDELINES

7.5.1 It is understood that per the NCI policy regarding the Requirements for the Research Use of Stored Human Specimens and Data, prospective NIH IRB approval and continuing IRB oversight must be obtained for research involving identified or coded samples or data where investigators can identify the source. This policy applies to research protocols where the remaining research activities are limited to data analysis and to the subsequent research use of specimens or data previously collected under a now terminated protocol. The following guidelines describe how these principles apply to this specific protocol.

7.5.2 Many samples on this study will be processed and stored in the AIDS Monitoring Laboratory (AML) run by Leidos Biomedical Research, Inc. in the NCI-Frederick facility located with Fort Detrick. The samples are stored under code, and the information linking these unique codes to the patients is kept on the AML database. The laboratory informatics system conforms to NIH Information Technology Security Requirements and NIH Protection of Human Research Subjects Guidelines. All laboratory staff is trained to adhere to NIH Information Technology Security Requirements and NIH Protection of Human Research Subjects Guidelines. Computers used to access inventory systems require username and password for login. The laboratory database is housed in a secure, protected environment and backups are performed routinely. Access to specimen information, clinical data, and stored specimens is limited to approved laboratory staff and the investigator in charge of the study (or individuals authorized by the investigator).

AIDS Monitoring Laboratory  
Leidos Biomedical Research, Inc.  
Frederick National Laboratory for Cancer Research  
[name]  
[contact]

7.5.3 The protocol team will inform the AML staff when tests are to be run with the specimens, and the samples used for testing will be tracked by the AML. This information will in turn be shared with the protocol team. The research nurse on the study will be in charge of tracking this information for the protocol team.

7.5.4 Some of the specimens are sent to the laboratory of [name], also in the Leidos Biomedical Research, Inc. NCI-Frederick facility located with Fort

Detrick. The samples sent are coded by the protocol research team and have no patient identifiers. They are logged in by [name] laboratory and kept in a locked facility. They are run in batch when enough specimens are collected. Records are kept when the specimens are used for analysis.

- 7.5.5 [name]  
Leidos Biomedical Research, Inc.  
[name]  
Frederick, MD  
[contact]
- 7.5.6 A limited number of samples are sent to [name] laboratory. This is a locked laboratory, and a log is kept of the specimens and when they are utilized.
- 7.5.7 [name]  
[name]  
[name]  
[contact]
- 7.5.8 Clinical testing of all samples will be one in accordance to the protocol. The protocol team will inform the AML staff when tests are to be run with the specimens, and the samples used for testing will be tracked by the AML. This information will in turn be shared with the protocol team. The research nurse on the study will be in charge of tracking this information for the protocol team.
- 7.5.9 Many routine samples and a sample of the biopsy specimens are sent to the Clinical Pathology or Pathology Departments of the NIH Clinical Center. These samples will be handled according to the procedures of these departments.
- 7.5.10 If patients have co-enrolled on study 01-C-0038 (Collection of Blood, Bone Marrow, Tumor, or Tissue Samples from Patients with HIV Infection, KSHV Infection, Viral-related Pre-Malignant Lesions, and/or Cancer), then the samples may also be tested under the specifications of that study. Similarly, if patients have co-enrolled on other studies approved by the NCI IRB that call for maintaining and testing the samples, then they may be transferred to those studies.
- 7.5.11 At the termination of the study, if patients have co-enrolled on study 01-C-0038 (Collection of Blood, Bone Marrow, Tumor, or Tissue Samples from Patients with HIV Infection, KSHV Infection, Viral-related Pre-Malignant Lesions, and/or Cancer), then the samples will be transferred to that study unless the patients request that this not occur. Also, if patients have co-enrolled on other studies approved by the NCI IRB that call for maintaining the samples, then they will be maintained on those protocols. Otherwise, the unused samples will be destroyed.
- 7.5.12 The PI will report any loss or destruction of the samples to the IRB, and any new use of the samples, specimens, or data will require prospective IRB approval.

